5.4.5. Subgroup analyses

Subgroup analyses will be performed on the key secondary endpoints by the subgroup variables listed in Section 2.4.1. The same analysis as defined in Section 5.3.3 will be performed.

5.5. Other Secondary Endpoints

Other secondary endpoints will be summarized descriptively by intervention arm, by study phase (unless specified otherwise), timepoint and study part. No imputation rule will be used in case of missing data and the analysis will be based on observed cases. Statistical analyses of selected other secondary endpoints will be done with no adjustment for multiplicity.

The following on and off-treatment periods will be used for all secondary efficacy endpoints:

- For all HBV endpoints:
 - **On-treatment** will be defined as the time periods in which the participant receives any of the study interventions (JNJ-3989/placebo and/or NA).
 - **Off-treatment** will be defined as the periods when the participants do not receive any of the study interventions (JNJ-3989/placebo and NA).
- For all HDV endpoints:
 - **JNJ-3989 on-treatment** will be defined as the time period in which the participant receives JNJ-3989/placebo (regardless of continuing NA treatment).
 - **JNJ-3989 off-treatment** will be defined as the time period in which the participant is not receiving JNJ-3989 (regardless of continuing NA treatment).

The following on and off-treatment nadirs will be used for all secondary efficacy endpoints:

- **On-treatment nadir** will be defined as the lowest value during the on-treatment period up to the time of assessment.
- **JNJ-3989 on-treatment nadir** will be defined as the lowest value during the JNJ-3989 on-treatment period up to the time of assessment.
- **Off-treatment nadir** will be defined as the lowest value during the off-treatment period up to the time of assessment.
- **JNJ-3989 off-treatment nadir** will be defined as the lowest value during the JNJ-3989 off-treatment period up to the time of assessment.
- **Overall nadir** will be defined as the lowest value collected during the study up to the time of assessment.

A confirmed criteria means that the criteria should be fulfilled at 2 or more consecutive time points or at the last observed time point.

5.5.1. Definition

5.5.1.1. Binary Endpoints

The number and proportion of participants experiencing the endpoints defined in the following subsections will be calculated and summarized as specified in Section 5.5.2.1.

5.5.1.1.1. HDV RNA Decline and Normal ALT

The following individual and combined endpoints related to HDV RNA decline and normal ALT will be evaluated over time during the study intervention and follow-up phases:

- HDV RNA $\geq 2 \log_{10}$ IU/mL decline from baseline or TND in combination with normal ALT.
- HDV RNA $\geq 2 \log_{10}$ IU/mL decline from baseline or HDV RNA TND.
- HDV RNA $\geq 2 \log_{10}$ IU/mL decline from baseline in combination with normal ALT.
- HDV RNA $\geq 2 \log_{10}$ IU/mL decline from baseline or $< \text{LLOQ}$ in combination with normal ALT.
- HDV RNA $\geq 2 \log_{10}$ IU/mL decline from baseline or $< \text{LLOQ}$
- HDV RNA TND in combination with normal ALT.
- HDV RNA $< \text{LLOQ}$ in combination with normal ALT.
- HDV RNA $\geq 2 \log_{10}$ IU/mL decline from baseline.
- HDV RNA TND.
- HDV RNA $< \text{LLOQ}$
- ALT categorization ($\leq 1.0 \times \text{ULN}$, $> 1.0 \times \text{ULN}$ to $< 2.5 \times \text{ULN}$, $\geq 2.5 \times \text{ULN}$)

Those endpoints will be analyzed as observed case without imputation (for combined endpoints, in case one of the two individual parameters is missing for a specific timepoint, the endpoint will be considered missing for that timepoint).

5.5.1.1.2. HDV RNA Cut-offs

HDV RNA will be analyzed over time using binary endpoints on both absolute values and reductions from baseline

The cutoffs for HDV RNA absolute values are as follows:

- $< \text{LLOQ}$
 - $< \text{LLOQ TND}$
 - $< \text{LLOQ TD}$
- $> \text{LLOQ}$
- $< 2,000 \text{ IU/mL}$
- $< 10,000 \text{ IU/mL}$

- The cutoffs for HDV RNA reductions from baseline are as follows:
 - $\geq 1 \log_{10}$ IU/mL
 - $\geq 2 \log_{10}$ IU/mL
 - $\geq 3 \log_{10}$ IU/mL
 - $\geq 4 \log_{10}$ IU/mL

5.5.1.1.3. Virologic HDV RNA Breakthrough

Two types of HDV RNA breakthroughs will be defined using 2 distinct thresholds:

Confirmed JNJ-3989 on-treatment increase in HDV RNA of $>1\log_{10}$ IU/mL from JNJ-3989 on-treatment nadir in participants who did not have HDV RNA JNJ-3989 on-treatment nadir $< \text{LLOQ}$ or confirmed $>1\log_{10}$ IU/mL (i.e., 630 IU/ml) above LLOQ of the HDV RNA assay in participants who had HDV RNA JNJ-3989 on-treatment nadir $< \text{LLOQ}$.

Confirmed JNJ-3989 on-treatment increase in HDV RNA of $>2\log_{10}$ IU/mL from JNJ-3989 on-treatment nadir in participants who did not have HDV RNA JNJ-3989 on-treatment nadir $< \text{LLOQ}$ or confirmed $>2\log_{10}$ IU/mL above LLOQ of the HDV RNA assay in participants who had HDV RNA JNJ-3989 on-treatment nadir $< \text{LLOQ}$.

5.5.1.1.4. JNJ-3989 Off-Treatment HDV RNA Relapses

JNJ-3989 off-treatment HDV RNA relapse will be defined using 2 distinct rules:

- 1) In participants with HDV RNA $< \text{LLOQ}$ (i.e., 630 IU/ml) at EOT: Confirmed increase in HDV RNA of $> 1 \log_{10}$ IU/mL above the LLOQ JNJ-3989 off-treatment.
- 2) In participants with HDV RNA $> \text{LLOQ}$ at EOT: Confirmed increase in HDV RNA of $> 1 \log_{10}$ IU/mL from EOT HDV RNA value JNJ-3989 off-treatment.

5.5.1.1.5. JNJ-3989 Off-treatment HDV Clinical Flares

An JNJ-3989 off-treatment HDV clinical flare is defined as a confirmed increase in HDV RNA of $> 1 \log_{10}$ IU/mL above the LLOQ JNJ-3989 off-treatment and confirmed ALT and/or AST $\geq 3x$ ULN and $\geq 3x$ JNJ-3989 off-treatment nadir during the follow-up phase.

The start date of an JNJ-3989 off-treatment HDV clinical flare is defined as the minimum date between the date when the confirmed HDV RNA criterion is met and start date of the JNJ-3989 off-treatment biochemical flare.

The end date of a JNJ-3989 off-treatment HDV clinical flare is defined as either:

- The maximum date between HDV RNA increase returns to $\leq 1 \log_{10}$ IU/mL and the date when a 50% reduction from the peak ALT and/or AST level is reached.
- Or the date of JNJ-3989 treatment restart, whichever comes first.
 - 1 (Yes)= confirmed HDV RNA of $> 1 \log_{10}$ IU/mL above the LLOQ JNJ-3989 off-treatment and confirmed ALT and/or AST $\geq 3x$ ULN and $\geq 3x$ JNJ-3989 off-treatment nadir

- 0 (No) = otherwise
- 2 (Not applicable) = no JNJ-3989 off-treatment HDV RNA and/or ALT/AST quantitative measurements available.

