5.1.1. Virology Data Handling Rules

Those measurements collected from screening visit to the end of study will be handled according to the following rules in [Table 4](#).

Table 4: Data Handling Rules for HDV and HBV Virology and Serology Assessments

HDV parameter	LLOQ	ULOQ	Imputed Values	
			If value < LLOQ	If value > ULOQ
HDV RNA	For outside of China : LLOQ = 63 IU/mL LOD = 14 IU/mL	NA	For outside of China : Main imputation: If <LLOQ 31.5 IU/mL Exploratory Imputation: If LLOQ TD: 31.5 IU/ml If LLOQ TND: 15.75 IU/ml ^(a)	NA
HBV parameter	LLOQ	ULOQ	Imputed Values	
			If value < LLOQ	If value > ULOQ
HBsAg	0.05 IU/mL	124,925.00 IU/mL w/o dilution 249,750.00 IU/mL with dilution	0.025 IU/mL ^(a)	137,417.5 IU/mL ^{(b)(c)} w/o dilution 274,725.00 IU/mL ^(c) with dilution
HBeAg	0.11 IU/mL	1,400.00 IU/mL w/o dilution 7,000.00 IU/mL with dilution	0.055 IU/mL ^(a)	1,540.00 IU/mL ^{(b)(c)} w/o dilution 7,700.00 IU/mL ^(c) with dilution
HBcrAg	3.0 log ₁₀ U/mL	7.0 log ₁₀ U/mL w/o dilution 9.0 log ₁₀ U/mL with dilution	2.7 log ₁₀ U/mL	7.7 log ₁₀ U/mL ^{(b)(c)} w/o dilution 9.9 log ₁₀ U/mL ^(b) with dilution
HBV DNA	20 IU/mL For Roche CAP/CTM Assay 10IU/mL for Roche COBAS 6800 assay	170,000,000 IU/mL w/o dilution	If < LLOQ: 5 IU/mL	187,000,000 ^{(b)(c)} w/o dilution
HBV RNA	LLOQ = 2.939 log ₁₀ cp/mL (i.e 869 cp/mL) LOD = 1.398 log ₁₀ cp/mL (i.e 25 cp/mL)	NA	If < LOD or target not detected then 1.114 log ₁₀ cp/mL (13 cp/mL)	NA
Anti-HBs	5mIU/mL	10000.0 mIU/mL	2.5 mIU/mL ^(a)	11000.0 mIU/mL ^(b)

Key: NA=Not applicable

(a) LLOQ/2

(b) ULOQ+(ULOQ/10)

(c) If the original result > ULOQ, then take the re-test value (i.e. diluted result). If the diluted result is not available, use the imputed value indicated in this table

All other viral activity data with values <LLOQ which are not included in the data handling rules above will be imputed by the absolute value divided by 2.

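### The coded HDV clinical-flare rule counts a level above 1 log10 over the LLOQ with no rise from end of treatment, and the relapse rule labels the LLOQ as 630 IU/mL where Table 4 gives 63.

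*SAP*

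**What the plan says.** **Clinical flare (SAP 5.5.1.1.5).** The definition sentence begins "An JNJ-3989 off-treatment HDV clinical flare is defined as a confirmed increase in HDV RNA of" more than 1 log10 above the LLOQ. It adds confirmed ALT and/or AST of at least 3x ULN and at least 3x the JNJ-3989 off-treatment nadir. The coded line begins "1 (Yes)= confirmed HDV RNA of" and sets the same distance above the LLOQ, without the word increase. The flare starts at the earlier of the HDV RNA criterion date and the biochemical flare start. The virologic part of its end is "The maximum date between HDV RNA increase returns to" 1 log10 or less; no reference value is named.

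**Relapse (SAP 5.5.1.1.4).** There are two branches by status at end of treatment (EOT). The first covers participants below the LLOQ, with the parenthesis "i.e., 630 IU/ml) at EOT: Confirmed increase in HDV RNA of" more than 1 log10 above the LLOQ. The second covers those above the LLOQ and takes the rise as "IU/mL from EOT HDV RNA value JNJ-3989 off-treatment".

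**Breakthrough (SAP 5.5.1.1.3).** For a nadir below the LLOQ, the threshold is more than 1 log10, "i.e., 630 IU/ml) above LLOQ of the HDV RNA assay in participants who had HDV RNA JNJ-3989 on-treatment nadir" below the LLOQ.

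**Assay limits (SAP 5.1.1, Table 4), outside China.** "LLOQ = 63 IU/mL LOD = 14 IU/mL", with "Main imputation: If <LLOQ 31.5 IU/mL".

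**The concern.** An HDV clinical flare off JNJ-3989 should pair a virologic rebound with an ALT/AST flare. The coded line does not ask for a rebound. It asks whether HDV RNA is above a fixed level, and a participant can already be above that level when JNJ-3989 stops. An ALT/AST flare with another cause would then be reported as an HDV flare. The definition sentence and the coded line can therefore give two different counts from the same data.

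The related rules do not have this gap. Breakthrough splits by whether the nadir was below the LLOQ, relapse splits by EOT value, and the HBV virologic flare (5.5.1.1.11) measures the rise from EOT when HBV DNA was not below the LLOQ on treatment.

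The relapse rule has a separate labelling fault. HDV relapse is a listed secondary endpoint (Section 1.1), and time to relapse (5.5.1.3.2.1) uses the same definition, so a misread label would affect both.

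**Working it through.** **1. Reproduce 630.** The LLOQ is 63 IU/mL (Table 4, outside China). One log10 above is 63 x 10 = 630 IU/mL, and two log10 above is 63 x 100 = 6,300 IU/mL. The figure in 5.5.1.1.3 is reproduced exactly. As a value for the LLOQ itself, which is how 5.5.1.1.4 reads, 630 is ten times too high.

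**2. Apply the virologic part of the flare rule.** The coded line requires confirmed follow-up HDV RNA above 630. The split version is: EOT below 63, follow-up above 630; EOT at or above 63, follow-up more than 10 x EOT. Values are in IU/mL.

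| EOT | Follow-up | log10(follow-up/63) | log10(follow-up/EOT) | Coded line | With EOT split |
|---|---|---|---|---|---|
| 100 | 100 | 0.20 | 0 | not met | not met |
| 500 | 500 | 0.90 | 0 | not met | not met |
| 1,000 | 1,000 | 1.20 | 0 | met | not met |
| 10,000 | 10,000 | 2.20 | 0 | met | not met |
| 100,000 | 100,000 | 3.20 | 0 | met | not met |
| 100,000 | 20,000 | 2.50 | -0.70 | met | not met |
| 31.5 (imputed) | 700 | 1.05 | 1.35 | met | met |
| 100,000 | 1,100,000 | 4.24 | 1.04 | met | met |

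Attachment 1 treats screening HDV RNA below 1,000 IU/mL as a deviation, so an eligible participant still at the screening level is already above 630. So is a participant who fell 2 log10 from 100,000 to 1,000.

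**3. Flare dates.** With HDV RNA above 630 throughout follow-up, the HDV criterion is met at the first confirmed off-treatment visit. The start date takes the earlier of the two dates, so it can fall well before the ALT rise. The HBV clinical flare requires overlap, or a biochemical flare starting within 4 weeks after the virologic flare ends; the HDV flare states no such link. For the end date, suppose HDV RNA is stable at 100,000. Measured from the LLOQ, it stays 3.20 log10 above and does not return to 1 log10 or less. Measured from EOT, the increase is 0 throughout. The text does not say which applies.

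**4. Relapse rule with 630 read literally.**

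| EOT | Follow-up | LLOQ = 63 | 630 as EOT cut only (threshold >630) | 630 as LLOQ throughout (threshold >6,300) |
|---|---|---|---|---|
| 100 | 700 | no (0.85 log10) | relapse | no |
| 300 | 2,900 | no (0.99 log10) | relapse | no |
| 300 | 3,500 | relapse (1.07 log10) | relapse | no |
| 31.5 | 700 | relapse | relapse | no |
| 31.5 | 5,000 | relapse | relapse | no |

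Used only as the EOT cut, 630 changes the branch for EOT values of 63 to 630 and adds false relapses. It cannot lose any there, because a rise of more than 1 log10 from 63 or above always exceeds 630. Used as the LLOQ throughout, it loses true relapses. A value exactly at the LLOQ falls in neither branch as written.

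**The case against.** The best defence of the flare rule is that its definition sentence and its end-date rule both speak of an increase, and only the coded line omits it. That is correct, and it means the section does not plainly abandon the rise. It does not settle the matter: the coded line is the operational rule, no reference value is given for the increase, and the two wordings can produce different counts.

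For the 630 label, the defence is that it is probably a misplaced parenthesis. Table 4 and 5.5.1.1.3 resolve it, and the operative relapse threshold is written relative to the LLOQ. This also stands. Counts change only if the label is programmed as written, and losing true relapses requires 630 to serve as both the EOT cut and the base of the threshold.

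Three stronger readings are tempting, and the SAP does not support them:

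- **That everyone who stays viraemic meets the flare rule.** Stable viraemia between 63 and 630 IU/mL does not meet the virologic part. Viraemia alone is never a flare, because the ALT/AST criterion must also be met.
- **That about 70% of Arm 1 is exposed, as the complement of the 30% target response in Attachment 3.** That target is for the Week 48 primary endpoint, which also requires normal ALT. It gives neither the share without a virologic response nor HDV RNA levels in follow-up.
- **That counts will certainly be wrong.** That depends on which wording is programmed and on which participants have ALT/AST flares.

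The reach is also limited. HDV clinical flare is not listed among the endpoints in Section 1.1, the HBsAg/HDV RNA analysis that uses it (5.6.1.4) is optional and post hoc, and the study is now descriptive.

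**Conclusion.** Both faults stand in limited form. The coded flare line can be met with no rise in HDV RNA by anyone whose value stays above 1 log10 over the LLOQ, so an ALT/AST flare of any cause can be counted as an HDV clinical flare, with a start date that may be too early and an end date that has no reference. The relapse rule mislabels the LLOQ ten-fold against the SAP's own table; read literally, it misroutes EOT values of 63 to 630 IU/mL.

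The number of participants affected cannot be derived from the SAP. With 52 participants in total (22 in Part 1, 30 in Part 2), a few misclassified events would change a reported proportion. The figures of 63 and 630 assume the laboratory outside China; Table 4 as available shows no LLOQ for the laboratory in China. The rules should be corrected before follow-up data are analysed.

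**What to change.** **Flare (5.5.1.1.5).** Use the relapse split in the definition sentence, the coded line and the end date:

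- EOT below the LLOQ of the applicable assay: confirmed HDV RNA more than 1 log10 above that LLOQ.
- EOT at or above the LLOQ: confirmed rise of more than 1 log10 from the EOT value.
- End date: measure the return to 1 log10 or less against the same reference as the start.
- Leave the ALT/AST criterion unchanged.

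**Relapse (5.5.1.1.4).** Move the 630 IU/mL parenthesis so that it follows the threshold of 1 log10 above the LLOQ, and state that it applies to the assay with an LLOQ of 63 IU/mL. Write the second branch as at or above the LLOQ, so that every EOT value has a branch.

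Wording the rules relative to the applicable assay's LLOQ avoids applying 63 and 630 to samples from a laboratory with a different limit. The cost is SAP wording and derivation code; no new data are needed.

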5.5.1.1.6. JNJ-3989 Off-treatment Sustained HDV Response

A JNJ-3989 off-treatment sustained HDV response is defined by having HDV RNA TND during the FU phase after stopping JNJ-3989 regardless of continuing NA treatment.

Alternative JNJ-3989 off-treatment sustained HDV responses will be evaluated using the following definitions:

- Having HDV RNA < LLOQ during the FU phase
- Having HDV RNA TND with normal ALT during the FU phase
- Having HDV RNA < LLOQ and normal ALT during the FU phase
- HDV RNA > 2 log₁₀ IU/mL decline from baseline and normal ALT during the FU phase.

Participants with missing HDV RNA at a specific timepoint will be considered as non-responders for that timepoint. No imputation rule will be used in case of missing data.

5.5.1.1.7. HBsAg Seroclearance

HBsAg seroclearance (i.e quantitative HBsAg < LLOQ) will be evaluated at all time points when assessed, and analyzed as observed case without imputation, with emphasis at the following time points:

- At Week 48 (Also defined as KSE 4, see section 5.4.3)
- Week 96
- Week 144/EOT
- FU Week 24
- FU Week 48

Of note, HBsAg seroclearance may be achieved prior to the FU Week 12, 24, 36, or 48, respectively, but must be observed at the given week of interest.

Note that HBsAg seroclearance at Week 48 is used for one of the key secondary endpoints and specific imputation rules applied. However, for this analysis over time, HBsAg data at Week 48 will be treated similarly to the other timepoints, i.e no imputation will be done in case of missing value.

5.5.1.1.8. HBsAg Seroconversion

Seroconversion of HBsAg is defined as having achieved HBsAg seroclearance and appearance of anti-HBs antibodies.

The seroconversion will only be assessed at the time points when the anti-HBs antibodies assessment is available. If the HBsAg value is missing at that specific time point, then the non-missing lab test closest to that specific timepoint will be used. If the non-missing lab test before and after the specific timepoint fall equidistant from the target timepoint, the later one will be used to impute the missing value.

Appearance of anti-HBs antibodies is defined as a baseline anti-HBs antibodies (quantitative) <LLOQ and a post-baseline assessment \geq LLOQ. A sensitivity analysis will be conducted using the threshold of 10 mIU/mL, i.e. appearance of anti-HBs antibodies is defined as a baseline anti-HBs antibodies (quantitative) <10 mIU/mL and a post-baseline assessment \geq 10 mIU/mL.

5.5.1.1.9. Virologic HBV Breakthrough

Virologic HBV breakthrough is defined as having a confirmed on-treatment HBV DNA increase by $>1 \log_{10}$ from on-treatment nadir level in participants who did not have on-treatment HBV DNA <LLOQ or a confirmed on-treatment HBV DNA level >200 IU/mL in participants who had on-treatment HBV DNA <LLOQ.

In addition, participants who experience a virologic breakthrough followed by on-treatment biochemical flare (see Section 5.5.1.1.11) will be evaluated.

5.5.1.1.10. HBsAg, HBeAg and HBV DNA Cut-offs

HBsAg, HBeAg (only for participants HBeAg-positive at screening) and HBV DNA will be analyzed over time using binary endpoints on both absolute values, change (\log_{10} transformed) and reductions (\log_{10} transformed) on from baseline.

The cutoffs for HBsAg absolute values are as follows:

- <1000 IU/mL
- <100 IU/mL
- <10 IU/mL
- <1 IU/mL
- < LLOQ (0.05 IU/mL)
-

The cutoffs for HBsAg reductions from baseline are as follows:

- $\geq 1 \log_{10}$ IU/mL
- $\geq 2 \log_{10}$ IU/mL
- $\geq 3 \log_{10}$ IU/mL
- $\geq 4 \log_{10}$ IU/mL

The cutoffs for HBeAg **absolute** values are as follows:

- < 10 IU/mL
- < 1 IU/mL
- < LLOQ (0.11 IU/mL)

The cutoffs for HBeAg **reductions** from baseline are as follows:

- $\geq 0.5 \log_{10}$ IU/mL
- $\geq 1 \log_{10}$ IU/mL
- $\geq 2 \log_{10}$ IU/mL
- $\geq 3 \log_{10}$ IU/mL

The cutoffs for HBV DNA **absolute** values are as follows:

- <LLOQ
- < 2000 IU/mL
- > 2000 IU/mL

The cutoffs for HBV DNA **reduction** from baseline are as follows:

- $\geq 1 \log_{10}$ IU/mL
- $\geq 2 \log_{10}$ IU/mL
- $\geq 3 \log_{10}$ IU/mL
- $\geq 4 \log_{10}$ IU/mL

5.5.1.1.11. HBV Flares

The criteria based on blood markers/lab tests for each of the flare types are defined as below.

a) HBV Virologic flare is defined as follows:

Derivation 1. This derivation of virologic flare will be assessed only for those participants who are off-treatment and had HBV DNA <LLOQ at the last observed point on-treatment.

The start date of a confirmed virologic flare is defined as the first date of two consecutive visits with HBV DNA > 200 IU/mL. The end date of the same confirmed virologic flare is defined as the first date when HBV DNA value returns to ≤ 200 IU/mL or the date of treatment restart (ie JNJ-3989 and/or NA), whichever comes first. Each virologic flare will be categorized based on the confirmed (ie two consecutive values) peak HBV DNA above any of the three thresholds within the start and end date of that flare as follows: 20,000 IU/mL 2,000 IU/mL and 200 IU/mL.

- 1 (Yes) = confirmed HBV DNA > peak threshold
- 0 (No) = at least one off-treatment HBV DNA measurement available and not meeting the criteria of confirmed HBV DNA > peak threshold.
- 2 (Not applicable) = no off-treatment HBV DNA quantitative measurements available.

Derivation 2. This derivation of virologic flare will be assessed only for those participants who are off-treatment and had HBV DNA \geq LLOQ at the last observed point on-treatment.

The start date of a confirmed virologic flare is defined as the first date of two consecutive visits with HBV DNA log₁₀ increase > 1 log₁₀ from EOT. The end date of the same confirmed virologic flare is defined as the first date when HBV DNA log₁₀ increase from EOT returns to \leq 1 log₁₀ or the date of treatment restart (ie JNJ-3989 and/or NA), whichever comes first. Each virologic flare will be categorized based on the confirmed (ie, two consecutive values) peak HBV DNA increase above any of the three thresholds within the start and end date of that flare as follows: 1 log₁₀, 2log₁₀, 3 log₁₀.

- (Yes) = confirmed HBV DNA increase from EOT > peak threshold
- 0 (No) = at least one off-treatment HBV DNA measurement available and not meeting the criteria of confirmed HBV DNA increase from EOT > peak threshold.
- 2 (Not applicable) = no off-treatment HBV DNA quantitative measurements available.

b) Off-treatment HBV biochemical flare is defined as follows:

The start date of a confirmed off-treatment biochemical flare is defined as the first date of two consecutive visits with ALT and/or AST \geq 3x ULN and \geq 3x nadir (ie, lowest value observed up to the start of the flare). The end date of the same off-treatment biochemical flare is defined as the first date when there is a 50% reduction from the peak ALT and/or AST level or the date of treatment restart (ie JNJ-3989 and/or NA), whichever comes first.

- 1 (Yes) = confirmed ALT and/or AST \geq 3x ULN and \geq 3x nadir (ie, lowest value observed up to the start of the flare)
- 0 (No) = otherwise

c) On-treatment HBV biochemical flare is defined as follows:

The start date of a confirmed on-treatment biochemical flare is defined as the first date of two consecutive visits with ALT and/or AST \geq 3x ULN and \geq 3x nadir (ie, lowest value observed up to the start of the flare). The end date of the same on-treatment biochemical flare is defined as the first date when there is a 50% reduction from the peak ALT and/or AST level, regardless of stopping JNJ-3989 and/or NA.

- 1 (Yes) = confirmed ALT and/or AST \geq 3x ULN and \geq 3x nadir (ie, lowest value observed up to the start of the flare)
- 0 (No) = otherwise

d) HBV Clinical flare is defined as follows:

A HBV clinical flare occurs either when a HBV virologic flare and off-treatment HBV biochemical flare overlap in time or when a HBV biochemical flare starts within 4 weeks following the end of a HBV virologic flare.

The start date of a HBV clinical flare is defined as the minimum start date of the HBV virologic flare and HBV biochemical flare. The end date of a HBV clinical flare is defined as the maximum end date of the HBV virologic flare and HBV biochemical flare, ie, the later date between HBV DNA returns to ≤ 200 IU/mL (or $\leq 1 \log_{10}$) and 50% reduction from the peak ALT and/or AST level reached during the HBV biochemical flare.

- 1 (Yes) = confirmed HBV DNA $>$ peak threshold (for derivation 1 of virologic flare) or HBV DNA increase from end of treatment $>$ peak threshold (for derivation 2 of virologic flare) and confirmed ALT and/or AST $\geq 3x$ ULN and $\geq 3x$ nadir (ie, lowest value observed up to the start of the flare)
- 0 (No) = otherwise

The HBV virologic and clinical flares will be assessed only off-treatment, while biochemical flares will be identified on-treatment and off-treatment, respectively. On-treatment virologic flares are described as virologic HBV breakthrough in Section [5.5.1.1.9](#).

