2. GENERAL ANALYSIS DEFINITIONS

The SAP will use throughout the document the following definitions:

- Study treatment refers to: JNJ-3989, placebo, or NA [entecavir (ETV), tenofovir disoproxil (TD), or tenofovir alafenamide fumarate (TAF)]
- Study agent refers to: JNJ-3989 or placebo
- Study intervention arm refers to:
 - Arm 1: JNJ-3989 (100 mg) + NA
 - Arm 2: Placebo + NA

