2.1. Analysis Phases and Visit Windows

2.1.1. Analysis Phase

The analysis phases are defined in [Table 1](#) below.

Table 1: Analysis Phases Start and End Dates

Analysis phase	Start date	End date
Screening	The date of signing the informed consent	1 day before the first study agent intake
Double-Blind (DB) Study Intervention	Date of first study agent intake	
If participant did not withdraw from the study and did not discontinue treatment early prior to the projected/actual Week 52 Visit date:
 
Min(Date of Week 52 study agent intake – 1 day, cut-off date*)
 
Otherwise:
 
[Min (Early study withdrawal visit date, study agent discontinuation date) + 5 days^a] or cut-off date*, whichever occurs first

Open-Label (OL) Study Intervention	
If participant has a projected/actual Week 52 Visit date:
 
 – End date of DB study intervention phase + 1 day 
Otherwise:
 
 – Missing 	
If participant did not withdraw from the study prior to the projected/actual Week 144 (Arm 1)/Week 148 (Arm 2) Visit date and did not discontinue treatment early prior to the projected/actual Week 140 (Arm 1)/Week 144 (Arm 2) Visit date:
 
[Min (Date of Week 144 Visit (for Arm 1) or / Date of Week 148 Visit (for Arm 2))+ 5 days^a] or cut-off date*, whichever occurs first
 
if participant withdrew from the study or discontinued treatment between projected/actual Week 52 Visit date + 1 day and projected/actual Week 144 (Arm 1)/Week 148 (Arm 2) Visit date:
 
[Min (Early study withdrawal visit date, study agent discontinuation date)+ 5 days^a] or cut-off date*, whichever occurs first

Follow-up	
If participant did not withdraw informed consent during DB or OL study intervention phases
 
Max (End date of DB study intervention phase, End date of OL study intervention phase) + 1 day
 
Otherwise:
 
Missing
	
If participant entered the Follow-up phase:
 
Max [early study withdrawal visit date, study completion date] or cut-off date, whichever occurs first.
 
Otherwise:
 
Missing

*Cut-off dates will be defined to match the prespecified timepoints for IDMC safety monitoring, interim analysis, the primary analysis and the final analysis, respectively.

^a: Addition of 5 days is only applicable for Adverse Events and Concomitant Medications

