Open-Label (OL) Study Intervention	365	52	Week 52	[352, 372]	
	379	54	Week 54	[373, 386]	
	393	56	Week 56	[386, 407]	
	421	60	Week 60	[408, 435]	
	449	64	Week 64	[436, 463]	
	477	68	Week 68	[464, 491]	
	505	72	Week 72	[492, 519]	
	533	76	Week 76	[520, 547]	
	561	80	Week 80	[548, 575]	
	589	84	Week 84	[576, 603]	
	617	88	Week 88	[604, 631]	
	645	92	Week 92	[632, 659]	
	673	96	Week 96	[660, 687]	
	701	100	Week 100	[688, 715]	
	729	104	Week 104	[716, 743]	
	757	108	Week 108	[744, 771]	
	785	112	Week 112	[772, 799]	
	813	116	Week 116	[800, 827]	
	841	120	Week 120	[828, 855]	
	869	124	Week 124	[856, 883]	
	897	128	Week 128	[884, 911]	
	925	132	Week 132	[912, 939]	
953	136	Week 136	[940, 967]		
981	140	Week 140	[968, 995]		
1009	144	Week 144 ^(b)	Not Applicable	[996, 1023]	

Phase	Target day	Analysis time point (Week)	Analysis time point (label)	Time interval (days) for Arm 1	Time interval (days) for Arm 2 ^(a)
	last visit during the intervention phase	149*	EOT ^(b)		
Follow-Up (FU)	15	150	Follow-up Week 2	[1, 22]	
	29	152	Follow-up Week 4	[23,36]	
	43	154	Follow-up Week 6	[37, 50]	
	57	156	Follow-up Week 8	[51, 71]	
	85	160	Follow-up Week 12	[72, 99]	
	113	164	Follow-up Week 16	[100, 127]	
	141	168	Follow-up Week 20	[128, 155]	
	169	172	Follow-up Week 24	[156, 190]	
	211	178	Follow-up Week 30	[191, 232]	
	253	184	Follow-up Week 36	[233, 274]	
	295	190	Follow-up Week 42	[275, 316]	
	337	196	Follow-up Week 48	[317, +∞]	
		last visit in the study	999*	EOS	

(a) Participants randomized to Arm 2 (placebo + NA) will have additional assessments during the OL phase at Week 54 and Week 144. See Protocol Section 1.3.2 for more details

(b) For participants who completed the OL phase (see Table 1), EOT corresponds to Week 144 Visit Date for Arm 1 and Week 148 for Arm 2

*End of treatment (EOT) visit will be the last post-baseline visit in double-blind or open-label phase, and End of study (EOS) visit (last available data during the follow-up) will be the last visit in the study.

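### HBV virologic flare Derivation 2 selects on the last on-treatment HBV DNA (NA included) but measures the rise from EOT, so flares can be misclassified in participants who stop NA after EOT

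*SAP*

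**What the plan says.** **Treatment periods for HBV endpoints (SAP 5.5).** The on-treatment state "will be defined as the time periods in which the participant receives any of the study interventions (JNJ-3989/placebo and/or NA"); either one is enough. Its counterpart, the off-treatment state, "will be defined as the periods when the participants do not receive any of the study interventions (JNJ-3989/placebo and NA"); both must have stopped. A participant on NA alone is therefore still on-treatment.

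**Who enters Derivation 2 (SAP 5.5.1.1.11 a).** Off-treatment participants with HBV DNA at or above "LLOQ at the last observed point on-treatment".

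**What is measured.** The start date, end date, peak category (1, 2 or 3 log10) and coding all use the change from EOT; a yes is a "confirmed HBV DNA increase from EOT > peak threshold". The clinical flare coding in part d of the same section uses the same rise, counted from end of treatment.

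**What EOT is (SAP 2.1.3, Table 2 footnotes).** "End of treatment (EOT) visit will be the last post-baseline visit in double-blind or open-label phase". For participants who complete the open-label phase, "EOT corresponds to Week 144 Visit Date for Arm 1 and Week 148 for Arm 2". For those who stop early, Table 1 in SAP 2.1.1 closes the double-blind or open-label phase at "Min (Early study withdrawal visit date, study agent discontinuation date"), and SAP 2 states: "Study agent refers to: JNJ-3989 or placebo". NA does not enter this date.

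**NA after EOT (SAP 4.6).** NA exposure is computed for the follow-up phase, with a date of NA discontinuation in the formula. Participants who stopped NA at Week 144/148 and did not restart count as zero weeks, so the plan allows for others with NA exposure in follow-up.

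**The concern.** Selection and measurement rest on two different visits whenever NA outlasts JNJ-3989/placebo and is then stopped. Selection follows the HBV convention, in which NA counts as treatment. The reference value follows the study phases, which close on JNJ-3989/placebo.

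The neighbouring rules do not have this problem. The HDV relapse rule in SAP 5.5.1.1.4 uses EOT both to classify participants and as the reference, and its off-treatment period also refers to JNJ-3989. HBV Derivation 1 uses an absolute threshold of 200 IU/mL and needs no reference value. Only Derivation 2, and the clinical flare that draws on it, mixes the two conventions.

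What is at stake is the classification of HBV virologic flare, and through it clinical flare, after all study treatment has stopped. These are listed secondary endpoints in a study of 52 participants, where one or two changed classifications would be visible in a proportion.

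**Working it through.** The SAP states no figure for this rule that could be reproduced. The check applies the rule to assumed HBV DNA profiles with each reference in turn.

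**Inputs from the SAP**
- A flare needs two consecutive off-treatment visits with a rise above 1 log10 (5.5.1.1.11).
- HBV DNA below LLOQ is set to 5 IU/mL; LLOQ is 20 or 10 IU/mL depending on the assay (Table 4).

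**Assumed inputs.** The HBV DNA values below are illustrative. Every last-NA value is at or above 20 IU/mL, so each profile enters Derivation 2 under either assay.

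**Formulas.** Let E be HBV DNA at EOT, L the last on-treatment value (on NA), and F the confirmed off-treatment value.
- Rise as written: log10(F/E)
- Rise from the value used for selection: log10(F/L)
- Rise from L minus rise from E: log10(E/L), whatever F is

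| E | L | F | log10(F/E) | log10(F/L) | Effect of using EOT |
|---|---|---|---|---|---|
| 2,000 | 30 | 15,000 | log10(7.5) = 0.88 | log10(500) = 2.70 | flare missed |
| 2,000 | 30 | 1,000 | log10(0.5) = -0.30 | log10(33.3) = 1.52 | flare missed |
| 500 | 30 | 15,000 | log10(30) = 1.48 | log10(500) = 2.70 | flare in both, category 1 instead of 2 |
| <LLOQ (5) | 25 | 60 | log10(12) = 1.08 | log10(2.4) = 0.38 | flare created |
| <LLOQ (5) | 40 | 300 | log10(60) = 1.78 | log10(7.5) = 0.88 | flare created |
| 100 | 100 | 1,500 | log10(15) = 1.18 | 1.18 | none |
| 100 | 100 | 900 | log10(9) = 0.95 | 0.95 | none |

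The discrepancy depends only on the movement between the two visits. For 2,000 to 30 it is log10(2,000/30) = 1.82; for 5 to 25 it is log10(5/25) = -0.70. Both are large against a 1 log10 threshold. A fall in HBV DNA on continued NA hides flares, and a rise creates them. With no movement the classification is the same.

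The fourth profile also shows an internal oddity: a flare is declared at 60 IU/mL, while Derivation 1 requires more than 200 IU/mL in participants who were below LLOQ at their last on-treatment observation.

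**Who is exposed.** All of the following must hold: NA continues past EOT; NA is then stopped during follow-up; HBV DNA is at or above LLOQ at the last NA observation; off-treatment values exist to assess; and HBV DNA moved enough between EOT and the last NA visit to cross a threshold. For a completer who stops NA at Week 144/148, EOT is the last on-treatment visit, so E and L are the same value.

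**The case against.** **Limited reach.** A reader might infer that flares are miscounted in anyone who continues NA beyond EOT. The SAP does not support that. The last paragraph of 5.5.1.1.11 assesses virologic and clinical flares only off-treatment, which by 5.5 requires NA to be stopped as well. A participant who stays on NA to the last visit is never assessed. The NA stopping point that the SAP names, Week 144/148, coincides with EOT for completers. This objection stands and bounds the point.

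**Frequency.** A reader might also infer that this is a common path because ALT elevations led to discontinuation criteria. The amendment history reports ALT elevations in about 50% of 22 Part 1 participants, but the SAP counts neither JNJ-3989 discontinuations nor later NA stops. Stopping JNJ-3989 early is not enough; NA must be stopped after EOT. The rationale for SAP Amendment 4 mentions guidance to continue NA to the last visit, which would make such cases fewer.

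**EOT may mean the end of all treatment.** The flare section counts restart of JNJ-3989 and/or NA as treatment restart, and 5.6.1.4 names JNJ-3989 explicitly where only that is meant. This reading would remove the problem, but it conflicts with the definition of EOT in 2.1.3, so a clarifying sentence would still be needed.

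**Invented values.** The profiles are assumed and show only that the rule can fail in both directions. A change in clinical flare also needs a qualifying off-treatment ALT/AST flare, which the profiles do not address.

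**Conclusion.** The point holds in a limited form. Derivation 2 selects participants on one visit and measures the rise from another. Where NA is stopped after EOT and HBV DNA changed in between, flares can be missed, created or miscategorised, and the clinical flare inherits this. The conclusion rests on EOT as defined in SAP 2.1.3 and on follow-up including participants who stop NA after EOT, which SAP 4.6 provides for but does not count. In the assumed profiles the discrepancy reaches 1.82 log10 in one direction and, for 5 against 40 IU/mL, log10(5/40) = -0.90 in the other. The number of participants affected cannot be derived from the SAP and could be small or zero.

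The consequence is limited: this is one derivation of an other-secondary endpoint in a study now analysed descriptively. It is still an inconsistent rule rather than an omitted detail, and worth correcting before the final analysis.

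**What to change.** In Derivation 2, measure the increase from the last observed on-treatment HBV DNA value before the start of that off-treatment period, the same value used for selection. Apply this to the start date, end date, peak category and coding, and to the corresponding clinical flare coding and end date in part d.

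The off-treatment period has to be named because SAP 5.5 speaks of periods in the plural, and 4.1 and 5.5.2.1.4 anticipate NA re-treatment; otherwise the last on-treatment value is not unique.

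The cost is SAP wording and the matching derivation code. No new data are needed and no clinical rule is touched. For participants who stop NA at EOT and have an HBV DNA value at that visit, nothing changes; if that value is missing, the new wording supplies a reference that the present text lacks.
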